**Investigational Product(s):**

ASP8062 5 and 25 mg tablets

**Dose(s):**

30 mg QD (1 x 25 mg tablet and 1 x 5 mg tablet).

**Mode of Administration:**

As a single oral dose to be taken preferably in the morning with or without food.

**Comparative Drug(s):**

Matching placebo for ASP8062 tablets.

**Dose(s):**

2 placebo to match ASP8062 tablets.

**Mode of Administration:**

As a single oral dose to be taken preferably in the morning with or without food.

**Rescue Therapy:**

If a subject experiences intolerable pain due to fibromyalgia during the baseline, treatment or follow-up periods, the subject should be instructed to use acetaminophen (for non-fibromyalgia pain, NSAIDs may be used as needed, refer to section 5.1.3 Concomitant medication).

Subjects are instructed to document all acetaminophen use in the e-diary under rescue medication.

**Dose(s):**

The maximum amount of acetaminophen is up to 1000 mg per dose, not to exceed 3000 mg/day.

**Mode of Administration:**

Oral

**Concomitant Medication Restrictions or Requirements:**

Medications taken for fibromyalgia during the 12 months prior to Screening and other medication taken 28 days prior to the Screening visit and up to the first dose of study medication (treatment period) will be documented in the appropriate case report form as prior medication. Subjects taking prohibited medications who are willing to discontinue these medications as medically indicated and based upon the Investigator's recommendation, may wash-out over a period of 5 half-lives on a schedule determined by the Investigator.

Medications taken after the first dose of study medication and up to EOS will be documented on the appropriate case report form as concomitant medication.

Prior and concomitant medications to be documented include but are not limited to: vitamins, herbal remedies (e.g., St. John's wort, valerian), OTCs and prescription medications. Any medications taken for treatment of pain symptoms will be documented as such on the case report form.

Subjects are instructed not to take any concomitant medication without first consulting the Investigator or study coordinator (SC) throughout the duration of the study.

**Concomitant Medication for Treatment of Non-Fibromyalgia Pain Symptoms:**

Nonsteroidal anti-inflammatory drugs (NSAIDs) will be allowed (with the exception of celecoxib), as needed, for treatment non-fibromyalgia pain, such as headache.

### **Prohibited Therapies:**

Concomitant use of the following medications, therapies or surgical procedures could influence the evaluation of the study drug's efficacy and safety and are prohibited throughout the study (wash-out through the EOS):

- Medications that may have efficacy in reducing pain in fibromyalgia (except for allowed rescue medication), for example: gabapentinoids, antidepressants (except for selective serotonin reuptake inhibitors), ketamine, GABAB receptor agonists (including sodium oxybate), opioids, celecoxib, chronic non-narcotic analgesics (with the exception of low dose aspirin for cardioprophylaxis, up to 325 mg daily) and topical pain medications.
- CYP3A4 inhibitors (including most protease inhibitors, most antifungals, calcium channel blockers, cimetidine, select antibiotics, grapefruit and/or grapefruit juice).
- CYP3A4 inducers (including phenytoin, carbamazepine, and St. John's wort).
- Use of cannabinoids from the Screening visit and throughout the study.
- Procedures that may have efficacy in reducing pain in fibromyalgia, for example: nerve block, iontophoresis, laser therapy, acupuncture, tender point injections, dry needle injections, spinal cord stimulation therapy, transcutaneous electrical nerve stimulation.
- Hypnotics other than those specified with restrictions in the following section on Permitted Medications.
- Tranquilizers, sedating antihistamines (non-sedating antihistamines are permitted), benzodiazepines for sedative, anxiolytic, or sleep aid. In contrast, non-benzodiazepines such as zolpidem are allowed for insomnia as discussed below in the section: Permitted Medication.

### **Permitted Medications:**

This list is not all inclusive and the Medical Monitor should be contacted to discuss medications not listed below.

- The following serotonin reuptake inhibitors will be allowed if the subject is on a stable dose 60 days prior to Screening and no changes are anticipated during the course of the study: sertraline, paroxetine, fluoxetine, citalopram, escitalopram, fluvoxamine, vilazodone, vortioxetine.
- The following medications will be allowed if they are stable for at least 30 days prior to Screening and no additional medication is taken for insomnia: zolpidem up to 10 mg, eszopiclone up to 1 mg, zaleplon up to 10 mg, zopiclone up to 2 mg, and melatonin for sleep.
- Allowed stable medications (i.e., stable dose 30 days prior to Screening and with no changes anticipated during the course of the study): anti-diabetic medications, anti-hypertensive medications, non-sedating antihistamines, lipid-lowering agents, asthma medications, low dose aspirin for cardioprophylaxis, non-sedating treatments for allergic rhinitis, triptans, multivitamins, short-term use of nasal, inhaled, and topical corticosteroids.

NSAIDs will be allowed (with the exception of celecoxib), as needed, for non-fibromyalgia pain, such as headache. However, chronic use of NSAIDs is not allowed (with the exception of low dose aspirin for cardioprophylaxis, up to 325 mg daily).

### **Permitted Non-Medication Therapy:**

The following therapies must be stable for at least 30 days prior to Screening and with no changes anticipated during the course of the study: exercise routines, chiropractic care, physical therapy, psychotherapy, massage therapy.

### **Duration of Study and Treatment:**

Subjects will be treated for a period of up to 8 weeks. Total study duration for a subject is approximately 18 weeks, including a Screening period of up to 6 weeks, an 8-week double-blind treatment period, and a 4-week follow-up period.

**Endpoints for Evaluation:**

Primary Efficacy

- Change from baseline to Week 8 in mean daily average pain score assessed by NRS (0 to 10 scale) in the subject's daily e-diary.

Secondary Efficacy

- Subject's response defined as achieving  $\geq 30\%$  reduction from baseline to Week 8 and EOT in mean daily average pain score assessed by NRS (0 to 10 scale) in the subject's daily diary.
- Subjects response defined as achieving  $\geq 50\%$  reduction from baseline to Week 8 and EOT in mean daily average pain score assessed by NRS (0 to 10 scale) in the subject's daily diary.
- Change from baseline to Weeks 2, 4, 8, and EOT in the FIQR Physical Function, Symptoms, and Overall Impact subscales.
- Overall subject improvement assessed by Patient Global Impression of Change (PGIC) at Weeks 2, 4, 8, and EOT.

### Safety and Tolerability Endpoints

- Treatment-emergent adverse events (AEs)/serious adverse events (SAEs) from Screening until EOS.
- Safety laboratory tests at Weeks 2, 4, 8 and 10.
- Vital signs at Weeks 2, 4, 8 and 10.
- 12-lead ECG parameters at Weeks 8 and 10.
- Physical examination at Weeks 8 and 10.
- C-SSRS (evaluation of suicidal ideation and behavior) at Weeks 2, 4, 8 and 10.

### **Statistical Methods:**

#### **Sample size justification:**

The sample size calculations are based on the primary efficacy endpoint of change from baseline to Week 8 in mean daily average pain NRS. A meta-analysis of the change from baseline in mean daily average pain NRS for pregabalin or duloxetine vs placebo in studies for fibromyalgia indicated an effect size of approximately 0.30.

Using an effect size of 0.39 (30% larger than the meta-analysis result) for the primary efficacy endpoint for the comparison of ASP8062 vs placebo, 84 subjects in the ASP8062 and placebo groups would be required to provide 80% power to demonstrate statistical significance using a 1-sided 5% significance level (based on the assumption of normally distributed data, and taking into account the interim analysis for futility).

The total number of subjects required for the analysis would be 168 (84:84 subjects in ASP8062: placebo). Assuming approximately 5% of randomized subjects will not contribute to the analysis, then a total of 178 subjects would be required for randomization using a 1:1 randomization ratio (89:89 subjects for the ASP8062: placebo groups).

#### **Efficacy:**

The primary endpoint is the change from baseline to Week 8 in the mean daily average pain NRS. The baseline mean daily average pain score will be derived from the daily average pain scores (based on the daily numerical rating scale [NRS] recorded in the 7 days before the first day of dosing). The primary analysis population will be the Full Analysis Set (FAS), which will include all randomized subjects who received at least 1 dose of study medication. Unless otherwise stated, all assessments of statistical significance will be one-sided at the 5% significance level, and as such one-sided p-values will be shown.

The primary analysis for the primary endpoint of change from baseline to Week 8 in the mean daily average pain NRS will use a mixed model repeated measures (MMRM) analysis, where the model will include the effects for treatment group, center (pooled where necessary), time (study Week 1 to

8) and treatment-by-time interaction, as well as the covariates of baseline mean daily average pain NRS and baseline pain-by-time interaction and subject as a random effect. The unconstrained between-time-point covariance structure will be used. This analysis will utilize observed data, and there will be no imputation for missing data. Least squares estimates for the primary endpoint will be shown for both treatment groups, and for the treatment comparisons of ASP8062 vs placebo (together with 2-sided 90% confidence intervals). A one-sided 5% significance level will be used for the comparison of ASP8062 vs placebo.

A sensitivity analysis for the primary endpoint will use the same MMRM model as described previously. However, for this secondary analysis, multiple imputation will be used for imputation of any missing data, using the 'Jump to Reference' algorithm (where placebo is the reference group) for subjects who discontinue due to lack of efficacy or AEs and standard regression-based multiple imputation for subjects with missing data for other reasons. An additional sensitivity analysis for the primary endpoint will use modified baseline observation carried forward (mBOCF) for missing data with analysis using ANCOVA, with covariates of baseline mean daily average pain NRS score and center (pooled where necessary). mBOCF is defined as imputation by baseline observation carried forward (BOCF) for subjects who discontinue due to lack of efficacy or AEs, and imputation by last observation carried forward (LOCF) for subjects with missing data at Week 8 for other reasons.

The primary analysis for the secondary endpoints, of mean daily average pain response ( $\geq 30\%$  and 50% reduction from baseline to Week 8 and to EOT) will be carried out with the Fisher's Exact Test (with one-sided p-value). In addition the percentage of subjects who meet cumulative response levels of  $> 0\%$  to  $= 100\%$  will be shown. For the Week 8 analysis subjects with missing data will be classified as non-responders (BOCF), and an additional analysis will use mBOCF. For the EOT analysis, LOCF will be used.

The primary analysis for the change from baseline to Weeks 2, 4 and 8 for the FIQR subscales of Physical Function, Symptoms and Overall Impact will use the same MMRM analysis as described above for the mean daily average pain score.

The primary analysis for the change from baseline to EOT for the FIQR subscales will use the same ANCOVA model as described above.

The primary analysis for the PGIC secondary endpoint will use the proportional odds model for ordinal data, with model term for treatment group. In addition, the percentage of subjects who achieve PGIC response ('Improved', 'Very Much Improved') will be carried out with the Fisher's Exact Test (with one-sided p-value) for binary data.

### **Safety:**

[figure not shown]
The safety variables will be summarized by descriptive statistics.

### **Interim analyses:**

Two interim analyses for futility based on the primary efficacy endpoint will be conducted. The timing of these analyses will be at approximately 35% and 55% of subjects with Week 8/EOT data. The plan for the interim analysis may be modified based on speed of recruitment. These analyses will be conducted by an Astellas statistician, with results reviewed by an Independent Data Monitoring Committee (IDMC). The Astellas statistician and other members of the Astellas IDMC are external to the study team. No one within the study team will be unblinded to the treatment allocation or interim results. Details of the interim analysis procedure, steps to maintain treatment blind in the study team and criteria for Stopping the study will be described in an Interim Analysis Plan (IAP).

## V. FLOW CHART AND SCHEDULE OF ASSESSMENTS

### Flow Chart

**Visit Day:** **-42**      -7      1      15      29      57      71      85

**Visit Week:** **-6 to -1**      -1      2      4      8      10      12

**Table 1 Schedule of Assessments**

Schedule of Assessments	Screening Period			Randomization	Treatment Period			Follow-Up Period a	
	Screening	Wash-out	Baseline Diary Run-In dd		Treatment			Follow-up Visit	End of Study (EOS) Phone Call
Visit	1	NA	2	3	4	5	6	7	N/A
Week		-6 through -1			2	4	8/EOT	10	12
Day (and Window)		-42 to -8		1	15 ± 2	29 ± 2	57 ± 2	71 ± 2	85 ± 2
ASSESSMENTS									
Informed Consent	X								
Demographics	X								
Height and Weight b	X			X		X	X		
Medical/Surgical History	X		X c						
Medication History and Concomitant Medication	X								
FM Diagnosis (ACR 1990 & 2010)	X								
Verify Eligibility Criteria (and duplicate subject database check)	X	X d	X d	X					
Phone Call to Subject e		X							X
e-diary Distribution/Return			X					X	
Physical Examination (including tender point exam at screening)	X			X			X	X	
Drug and Alcohol Screen f	X		X	X					
Randomization g				X					
Vital Signs h	X			X	X	X	X	X	
Laboratory Tests (Hematology, Biochemistry, Urinalysis) i	X			X	X	X	X	X	
Electrocardiogram j	X			X			X	X	
Pregnancy Test	X k			X l			X l	X l	
Blood Sample for Pharmacogenomics m				X					
Blood sampling for Pharmacokinetics n				X	X	X	X		

Table continued on next page

Schedule of Assessments	Screening Period			Randomization	Treatment Period			Follow-Up Period a	
	Screening	Wash-out	Baseline Diary Run-In dd		Treatment			Follow-up Visit	End of Study (EOS) Phone Call
	Visit	1	NA	2	4	5	6		
Week	-6 through -1				2	4	8/EOT	10	12
Day (and Window)	-42 to -8		-7 to -1	1	$15 \pm 2$	$29 \pm 2$	$57 \pm 2$	$71 \pm 2$	$85 \pm 2$
ASSESSMENTS									
CMSI			X						
MINI o	X								
HADS p	X			X			X		
NRS e-diary Collection q				←	█	█	█	→	
PGIC s					█	X	X	X	X
PGIS t				X	█	█	█	█	X
FIOR x	X			←	█	X	X	X	X
C-SSRS	X				█			█	
Subject Training Materials aa	X		X		X	X	X	X	X
Study Drug Dispensed					X	X	X		
Study Drug Dosing bb					X	X	X	X	
Study Drug Returned						X	X	X	
Adverse Events cc	←								→
Rescue Medication (if applicable)			←						→

- a) Follow-up visit and phone call will be planned relative to date of last dose (14 and 28 days post last dose).
- b) Height will be measured at screening only. Weight will be collected at screening, prior to randomization, week 4 and week 8/EOT.
- c) Any change between the screening and randomization visits will also be captured in the medical/surgical history.
- d) Continued subject eligibility to be confirmed based on laboratory results prior to having the subject wash-out of current pain medications (phone call). Continued subject eligibility to be confirmed based on completion of wash-out prior to having the subjects start baseline diary run-in (visit 2).

Footnotes continued on next page

- e) During screening period (wash-out): Study staff to contact the subject, if necessary, to initiate wash-out of current pain medications after continued eligibility has been confirmed. During follow up: Follow-up phone call 4 weeks (day 85) post study drug will be required.
- f) Subjects will be tested for drugs and alcohol at screening, baseline diary run-in and randomization. A positive test for tetrahydrocannabinol (THC) and/or opioids is allowed at the screening visit, but must be confirmed negative prior to baseline diary run-in and randomization.
- g) Continued subject eligibility to be assessed and confirmed based on daily average pain scores recorded in the e-diary prior to subject being randomized.
- h) Resting blood pressure and pulse rate values will be the average of the supine triplicates from the orthostatic measures for those days when orthostatic blood pressure is assessed. Pulse rate and blood pressure will be measured in triplicate after the subject has rested for at least 7 minutes in the supine position, each measurement approximately 1 minute apart (-3, -2, and -1 minutes before standing). Afterwards, the subject will be instructed to stand up within 10 seconds and remain free standing with no support on wall or furniture. Standing blood pressure and pulse rate will be measured after the subject has been in the free standing position at 3 minutes (every attempt should be made to take the measurement as close as possible to 3 minutes). Orthostatic vital signs will be captured on day 1 pre-dose and approximately 2 hours post dose and at week 8/EOT. Resting vital sign measurements should be collected at all other visits (except visit 2). All vital sign measurements should be conducted prior to blood draws. Body temperature will be assessed at screening, randomization and week 8/EOT only.
- i) Blood specimens for scheduled clinical chemistry laboratory tests do not need to be fasted samples.
- j) Electrocardiograms are to be conducted prior to blood draws. A single electrocardiogram (ECG) will be obtained at the specified visits, unless, in the investigator's judgment, additional ECG's are required for safety reasons.
- k) Serum for females of childbearing potential.
- l) Urine for females of childbearing potential. Sample is to be collected prior to randomization, and at week 8/EOT, and week 10/ follow-up visits.
- m) Sample to be collected one time, preferably prior to first dose on day 1; however, can be collected at any time during the course of the study. Separate pharmacogenomics informed consent will need to be obtained from subject prior to collecting.
- n) A single pharmacokinetic sample will be taken on day 1 in the clinic at approximately 1-4 hour(s) after dosing and once at each visit during weeks 2, 4 and 8/EOT. PK samples at weeks 2, 4, and 8/OT should be evenly split between the following 3 sampling windows: before dosing, 1-4 hours post dose and >4 hours post dose. Time of the last dose and time of sample collection will be captured in the eCRF during these visits.
- o) Mini-International Neuropsychiatric Interview (MINI) will be completed by site personnel at screening.
- p) Hospital Anxiety and Depression Scale (HADS). Questionnaire will be completed by the subject at screening, randomization and the week 8/EOT visits.
- q) Numeric Rating Scale (NRS). Subject is to rate average pain on a daily basis (24hour recall) by entering pain score (0 10) in the e-diary. The NRS should be completed prior to bedtime at a consistent time of day throughout the study starting daily at diary run-in until week 10.
- r) [REDACTED]
- s) Patient Global Impression of Change (PGIC). Questionnaire will be completed by the subject at week 2, 4 and 8/EOT follow-up visits.
- t) Patient Global Impression of Severity (PGI-S). Questionnaire will be completed by the subject at randomization and week 2, 4 and 8/EOT follow-up visits.
- u) [REDACTED]
- v) [REDACTED]
- w) [REDACTED]

*Footnotes continued on next page*

- x) Fibromyalgia Impact Questionnaire Revised (FIQR) will be completed by the subject at screening, randomization and at week 2, 4, 8/EOT and week 10/follow up visits. At screening, subject only completes the item for pain of the FIQR.
- y) [REDACTED]
- z) Columbia Suicide Severity Rating Scale (C-SSRS). Questionnaire will be facilitated by the Principal Investigator/Site staff, as appropriately trained, at screening, randomization, weeks 2, 4, 8/EOT, and week 10/follow up visits.
- aa) Subject Training Materials are to be distributed and reviewed during the screening period.
- bb) Subjects will begin study drug dosing on day 1 of the randomization visit.
- cc) (Serious) Adverse Events will be collected from the time of signing the informed consent through 4 weeks post-last dose.
- dd) The baseline diary run-in may be extended up to 2 days if necessary in the Investigator's opinion. In general, the Screening period should not exceed 42 days.

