### **5.4.1 Vital Signs**

Single measures of sitting resting blood pressure (SBP and DBP) and pulse rate values will be obtained at each visit (except for Visit 2) and should be conducted prior to blood draws. Blood pressure should always be measured on the same arm of the subject and preferably in the same position (sitting or supine).

Body temperature will be assessed at Screening, Randomization and Week 8/EOT only. The method of recording body temperature must be the same between visits (acceptable methods are oral or tympanic temperature).

Vital signs should be taken before scheduled blood draws.

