### **6.2.3 Vital Signs**

Vital signs variables are raw values (i.e., values at each scheduled visit) and changes from baseline in systolic blood pressure (SBP), diastolic blood pressure (DBP) and pulse rate at Day 1 2-hours post dose, Weeks 2, 4, Week 8/EOT and Week 10. Orthostatic SBP, DBP and pulse rate are assessed on Day 1 pre-dose, Day 1 2-hours post dose, Week 8/EOT (triplicate supine measurements approximately 1 minute apart [-3, -2, -1 minutes before standing] followed by a single standing measurement approximately 3 minutes after standing). Single resting measurements of SBP, DBP and pulse rate are measured on at Screening, Weeks 2, 4 and Week 10.

Orthostatic vital signs (SBP, DBP, pulse rate) will be derived for each subject as follows:

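### Protocol Section 5.4.1 and Table 1 footnote h give conflicting vital-signs procedures for Day 1 and Week 8/EOT, and the SAP's orthostatic analyses work only with footnote h

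*Protocol*

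**What the plan says.** **Protocol, Table 1, footnote h (attached to the Vital Signs row).** "Orthostatic vital signs will be captured on day 1 pre-dose and approximately 2 hours post dose and at week 8/EOT". The supine part reads: "Pulse rate and blood pressure will be measured in triplicate after the subject has rested for at least 7 minutes in the supine position". The standing part reads: "Standing blood pressure and pulse rate will be measured after the subject has been in the free standing position at 3 minutes". The footnote also fixes the resting value on those days: "Resting blood pressure and pulse rate values will be the average of the supine triplicates from the orthostatic measures".

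**Protocol, Section 5.4.1 (the vital-signs procedure).** The instruction to sites is: "Single measures of sitting resting blood pressure (SBP and DBP) and pulse rate values will be obtained at each visit (except for Visit 2"). This section has no triplicate, no standing reading and no post-dose time on Day 1, and it does not refer to Table 1. By contrast, Section 5.4.3 on laboratory tests does refer the reader to Table 1.

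**SAP, Section 6.2.3.** "Orthostatic SBP, DBP and pulse rate are assessed on Day 1 pre-dose, Day 1 2-hours post dose, Week 8/EOT". The same section places single resting readings at Screening and Weeks 2, 4 and 10 only. SAP Table 13 defines the orthostatic result as standing minus the supine average, and makes it missing when either part is absent. SAP Section 7.5.4 summarizes standing values, and SAP Table 24 counts orthostatic outliers at the Day 1 2-hour time point, at Week 8/EOT and over the double-blind period.

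**The concern.** Two current protocol texts govern the same measurement at Visit 3 (Day 1) and Visit 6 (Week 8/EOT). One sitting reading and the mean of three supine readings cannot both be the resting value. The section that a site would open to learn how vital signs are taken also does not tell it that standing and 2-hour readings exist.

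The rest of the protocol body does not repair this. The Visit 3 narrative in Section 2.2.1 lists vital signs before randomization and a post-dose pharmacokinetic sample, but no post-dose vital signs. The safety endpoints in Section 2.3.1 name Weeks 2, 4, 8 and 10. The vital-signs analysis in Section 7.5.3 does not mention orthostatic data. Footnote h is the only place in the protocol where the requirement appears.

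At stake is part of the safety picture. Safety and tolerability relative to placebo is a primary objective. Section 1.2 lists dizziness and lightheadedness among the most common possibly drug-related events in Phase 1, and gives tmax as 1.5 to 3 hours. The Day 1 2-hour set falls inside that range and is the only vital-signs reading with a specified post-dose time. Once missed, it cannot be recovered.

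**Working it through.** The plan states no figure to reproduce. The check sets the texts side by side and counts readings by hand.

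| Item | Table 1 footnote h | Section 5.4.1 | SAP |
|---|---|---|---|
| Occasions on Day 1 and Week 8/EOT | 3 (Day 1 pre-dose, Day 1 about 2 h, Week 8/EOT) | 2 (one per visit) | 3 (Section 6.2.3) |
| Readings per occasion | 3 supine + 1 standing | 1 sitting | 3 supine + 1 standing |
| Resting value on those days | mean of the supine triplicate | the single sitting reading | supine average (Table 13; Section 7.5.4) |
| Single resting readings | all other visits except Visit 2 | each visit except Visit 2 | Screening, Weeks 2, 4 and 10 |

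**Readings per subject over Day 1 and Week 8/EOT**

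- Footnote h: 3 occasions × (3 supine + 1 standing) = 12 readings, of which 3 × 1 = 3 are standing.
- Section 5.4.1: 2 visits × 1 = 2 sitting readings, with 0 standing and 0 supine triplicates.

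**Evaluable orthostatic results under SAP Table 13**

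- Footnote h: a supine average and a standing value on each of 3 occasions gives 3 of 3.
- Section 5.4.1 alone: both parts are absent on every occasion, which gives 0 of 3.

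A subject measured only by Section 5.4.1 therefore contributes nothing to the standing summaries, nothing to Table 24, and nothing to the Day 1 2-hour row of the resting summary.

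**Denominator.** With 178 randomized subjects, the full plan is 178 × 3 = 534 orthostatic sets, or 89 × 3 = 267 per arm, if every subject provides the Week 8/EOT set. This is the planned total. It is not an estimate of what would be lost.

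**Can both texts be followed?** For the standing and 2-hour readings, yes: Section 5.4.1 is silent on them and does not forbid them. For the resting value at Visits 3 and 6, no. A site that took both a sitting reading and the supine triplicate would hold two candidates for that value, and SAP Section 6.2.3 foresees no single resting reading on those days.

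**The case against.** The strongest reply is that no site works from Section 5.4.1 alone. The protocol's design section sends the reader to the Schedule of Assessments for visit procedures. Footnote h hangs on the Vital Signs row and is a complete instruction, with rest time, spacing of readings, time allowed to stand and time of the standing reading. Section 5.4.1 itself contemplates supine measurement: "Blood pressure should always be measured on the same arm of the subject and preferably in the same position (sitting or supine"). The SAP follows footnote h throughout, and its revision history confirms that the 2-hour reading was part of the working schedule. The eCRF and site instructions, which are not visible here, may prompt for the full set.

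Much of this stands. It makes study-wide loss unlikely, and it means that the documents do not show the data will be missing. It does not remove the conflict over the resting value. Allowing a supine position also supplies no triplicate, no standing reading and no 2-hour reading.

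Three stronger readings are tempting, and the documents do not support them.

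- **A percentage loss.** A reader might assume that some share of sites follows Section 5.4.1 and convert it into lost sets or a wider bound on an event rate. Nothing in either document supports any share.
- **A biased comparison.** Losses would cluster by site, so a reader might infer a distorted contrast between arms. Randomization is 1:1, double-blind and stratified by site, so a site's habit should fall on both arms about equally. Balance within a site is only approximate, at about 178/35 = 5.1 subjects per site. Safety is also summarized without hypothesis tests. The plausible harm is lower precision.
- **All orthostatic sets taken near peak concentration.** Only the Day 1 2-hour set is timed that way. The Day 1 pre-dose set precedes drug, and the Week 8/EOT set has no time relative to dose. Some readings at Weeks 2, 4 and 8 may also fall near tmax, because vital signs precede blood draws and one of the pharmacokinetic sampling windows is 1 to 4 hours after dosing.

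The listed vital-signs endpoint covers Weeks 2, 4, 8 and 10, so the Day 1 sets lie outside it, and symptomatic dizziness would still be captured as an adverse event. Both facts limit the weight of the point. They do not settle which procedure sites should use.

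**Conclusion.** The conflict is real and stands in current protocol text. Section 5.4.1 and Table 1 footnote h cannot both define the resting value at Visits 3 and 6, and the SAP's orthostatic derivations can use only the footnote h readings. The size is exact per subject: 12 readings and 3 of 3 evaluable orthostatic results under footnote h, against 2 readings, 0 of 3 and no Day 1 2-hour reading under Section 5.4.1 alone.

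Across the study the size is unknown. It depends on how many sites work from Section 5.4.1 without footnote h, and the documents give no basis for that number. The conclusion that any loss would mainly reduce safety precision rests on the stratified, blinded allocation and on site practice being the same for both arms. The point is more than clerical, because one of the two rules, if followed, empties a planned safety analysis for those subjects. It does not touch the primary efficacy analysis.

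**What to change.** Reconcile the passages by aligning protocol Section 5.4.1 with Table 1 footnote h and SAP Section 6.2.3:

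1. Limit the single resting reading in Section 5.4.1 to Screening and Weeks 2, 4 and 10.
2. For Day 1 (pre-dose and about 2 hours post-dose) and Week 8/EOT, either refer to footnote h or repeat its supine-triplicate and standing procedure, and state that the supine mean is the resting value on those days.
3. In the same pass, correct footnote h as reproduced in the SAP. It names only pulse rate for the supine triplicate, where the protocol's footnote names pulse rate and blood pressure.

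The cost is protocol and SAP wording plus a memo to sites. No assessment is added, since Table 1 already schedules every reading.
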